3.2 STUDY GROUPS AND RANDOMISATION

The two vaccine groups (Groups A and B) will be randomised 1:1 to one of two interventions (bivalent Omicron-specific Moderna and Novavax) stratified by age (<50 and ≥50 years). An independent statistician from the Melbourne Children's Trial Centre at the Murdoch Children's Research Institute will provide a secure, password-protected web-based randomisation schedule. Blocked randomisation will be used with random blocks of permuted length.

50% of participants from each vaccine group will be included in the cell-mediated immunity (CMI) subgroup analysis. We will ensure that the age strata (<50 and ≥50 years) are equally represented in the CMI vaccine groups.

The control group will not be randomised and will be recruited from participants <60 years of age who indicate that they are not planning to receive a fourth vaccine dose at the time of recruitment. Controls will be recruited into proportional pre-defined age bands (18-29 years, 30-49 years, 50-59 years).

Table 1. Study groups and strata

Group	Age group	Booster vaccine	Dose given	Number
Group A	<50 years	Bivalent Moderna BA.1	50µg	75
	<50 years	Bivalent Moderna BA.4-5	50µg	75
	≥50 years	Bivalent Moderna BA.4-5	50µg	75
Group B	<50 years	Novavax	50µg	150
	≥50 years	Novavax	50µg	75
Group C	<60 years	No vaccine	-	150

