9 ANALYSIS OF EXPLORATORY OUTCOMES

9.1 ANALYSIS OF BREAKTHROUGH INFECTION ENDPOINTS

Breakthrough infections will be defined in three ways:

- i) Documented infections (positive by RAT or PCR)
- ii) Undocumented infections: Defined as a fold-change of ≥ 1.2 in spike-specific SARS-CoV-2 Wuhan IgG results between visits (from Day-28 onwards)
- iii) Undocumented infections identified through N-Protein IgG

Table 12 lists the breakthrough infection endpoints, including the timepoint measured, population measure, groups being compared and the measure of association between groups.

Table 12. Breakthrough infection endpoints

Breakthrough Infection Endpoint	Outcome	Timepoint [#]	Population measure	Comparison	Measure of association
i.	Breakthrough infection [^]	To Day-28 visit; Month-6 visit; Month-12 visit; Month-18, Month-24, Month-30	Incidence risk	Group A vs Group B vs Group C	Descriptive only
ii.	Breakthrough infection [^] by time-period (<14 days, Day 14 – Day-28 visit, Day-28 visit – Month-6 visit, Month-6 visit – Month-12 visit, Month-12 visit – Month-18 visit, Month-18 visit – Month 24 visit, Month-24 visit – Month 30 visit)			Group A vs Group B vs Group C	Descriptive only

[#]Analysis to be repeated at each analysis timepoint, for the risk and rate of breakthrough infection to that timepoint.

[^]Analysis to be repeated for undocumented breakthrough infections determined through Spike and N-protein IgG.

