9.2 ESTIMAND-TO-ANALYSIS TABLES FOR BREAKTHROUGH INFECTION ENDPOINTS

Table 13. Generic Estimand-to-Analysis table for all breakthrough infection endpoints for incidence risk (specified in Table 12).

Exploratory objective (as per Protocol): To describe the number and severity of breakthrough cases in the control group compared with the two vaccine groups (bivalent Moderna and Novavax)	
Estimand (for each trial vaccine):	Incidence risk of [OUTCOME] [*] to [TIMEPOINT] [*] , by trial vaccine in adults 18 years or older who have received their third dose of COVID-19 vaccine at least six months previously
ESTIMAND Attributes:	Incorporation of Estimand Attribute in ANALYSIS:
Treatment Bivalent mRNA Moderna COVID-19 vaccine and protein-based Novavax COVID-19 vaccine	Study arms Bivalent Moderna vaccine arm Novavax vaccine arm Control arm
Adults 18 years or older who have received their third dose of COVID-19 vaccine at least six months previously	Analysis set All randomised participants
Variable SARS-CoV-2 infection (breakthrough infection)	Outcome measure 1. Breakthrough infection as determined by at least one positive SARS-CoV-2 test (PCR) [^]

	2. Undocumented BTI as defined as a fold-change of ≥ 1.2 in spike-specific SARS-CoV-2 Wuhan IgG results between visits
Handling of intercurrent events	
Event	Strategy⁴
Receipt of 5 th dose (self-initiated)	Treatment Policy (interpret results in conjunction with 5 th dose coverage)
Population-level summary measure	
Incidence risk (proportion positive)	

*This table is generic for all breakthrough infection endpoints for incidence risks (with varying combinations of outcomes and timepoints) specified in Table 12, as they will be analysed in the same way.

⁴Analysis to be repeated for undocumented breakthrough infections

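### The spike-IgG rule for undocumented breakthrough infection does not set apart intervals containing a COVID-19 vaccine dose, so a dose can be counted as an infection

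*SAP*

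**What the plan says.** SAP 9.1 defines breakthrough infection in three ways: by a positive test, by spike IgG and by N-protein IgG. The spike definition is a fold-change of at least "1.2 in spike-specific SARS-CoV-2 Wuhan IgG results between visits (from Day-28 onwards"). Table 12 asks for risk to each visit and risk by time-period in Groups A, B and C, and its footnote repeats the analysis for the spike and N-protein definitions.

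Table 13 restates the rule ("Undocumented BTI as defined as a fold-change of" 1.2 or more) without the Day-28 start point. It handles a self-initiated 5th dose by Treatment Policy, with the note "interpret results in conjunction with 5 th dose coverage". Its footnote applies the table to all breakthrough incidence-risk endpoints, "as they will be analysed in the same way".

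On doses, Protocol 7.2.1 and the Visit 10 section let vaccine-group and control participants take further COVID-19 vaccines before Month 30 and stay in the study. SAP 6.5 lists a 5th dose as an intercurrent event that raises immunological markers. On sampling, Protocol 7.2.4 and the summary of the blood schedule give controls no Day-28 blood.

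Two other pairs of statements do not match:
- SAP 9.1 has "Documented infections (positive by RAT or PCR"), while Table 13 has "Breakthrough infection as determined by at least one positive SARS-CoV-2 test (PCR").
- Table 13 lists a control arm but gives "Analysis set All randomised participants", while SAP 3.2 states "The control group will not be randomised and will be recruited from participants <60 years of age".

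**The concern.** Treatment Policy is coherent when the outcome is a positive test: a dose may change the risk of infection, but it does not turn a test positive. The spike rule is different, because its outcome is a rise in the antibody that the dose is meant to raise. Leaving post-dose samples in then allows the intercurrent event to be recorded as the outcome.

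The exploratory objective is to describe breakthrough cases in the controls against the two vaccine groups. If uptake of further doses differs between groups, spike-rule counts will tend to differ even where infection risk is the same. Controls may be the group most likely to differ, since they were recruited as people not planning a fourth dose but are free to change their minds. Table 13 has no entry for that case: a control's first extra dose is a 4th, and only a 5th is named.

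**Working it through.** **No stated figure to reproduce.** The 1.2 threshold is given without a derivation, and no sample size or power rests on it. The check is a reading of the text, with arithmetic for scale only.

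**1. Can a dose meet the rule?**
- The rule looks only at the ratio of consecutive Wuhan spike-IgG results (SAP 9.1).
- Further doses are allowed in every group (Protocol 7.2.1, Visit 10).
- A 5th dose raises these markers (SAP 6.5).
- Post-dose samples stay in under Treatment Policy, for every breakthrough endpoint (Table 13 and its footnote).

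So an uninfected participant whose IgG is still at least 1.2-fold higher at the draw after a dose is counted as infected.

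**2. Scale of the dose effect (all inputs assumed).** Let *p* be the share flagged through true infection, *f* the share of doses still showing a rise of at least 1.2-fold at the next draw, and Δu the difference in dose uptake between two groups. With dose and infection independent:

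shift in apparent risk = Δu × f × (1 − p)

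For Δu = 10 percentage points:
- f = 0.25, p = 0.40: 10 × 0.25 × 0.60 = 1.5 points
- f = 1.0, p = 0.10: 10 × 1.0 × 0.90 = 9.0 points

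The 1.5 is not a floor. If antibody wanes quickly, *f* falls below 0.25 and the shift goes towards zero.

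**3. Observation window.** Draws are at Day 0, Day 28 and Months 6, 12, 18, 24 and 30 in A/B; controls have the same draws without Day 28. Day 28 is 28/30.4375 = 0.92 months. The start-point phrase can be read in two ways for controls.

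| Window to | A/B | C, both samples from Day 28 on | C, Day 0 paired with Month 6 |
|---|---|---|---|
| Month 6 | 6 − 0.92 = 5.1 | 0 | 6 |
| Month 12 | 12 − 0.92 = 11.1 | 12 − 6 = 6 | 12 |
| Month 30 | 30 − 0.92 = 29.1 | 30 − 6 = 24 | 30.0 |

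For scale, assume the same constant rate of 1% to 3% per month in every group and risk = 1 − exp(−rate × window). Risk to Month 12 is 10.5% to 28.3% in A/B. In C it is 5.8% to 16.5% on the first reading. On the second it is 1 − exp(−0.12) = 11.3% to 1 − exp(−0.36) = 30.2%. The choice of pair therefore decides whether the windows differ materially.

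Table 13 omits the start point altogether. Read alone, it would let the A/B rise from baseline to Day 28, after the trial vaccine, count as infection.

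**4. Test and denominator.** Protocol 7.2.8 (Unscheduled visits) asks participants with symptoms to take a RAT and documents all positive RATs, so the PCR-only wording in Table 13 does not match how cases are found. Controls are not randomised, so Table 13's analysis set, taken literally, omits an arm the same table lists.

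**The case against.** The strongest reply is that doses are already in view. Table 13 asks for results to be read with 5th-dose coverage, Dummy Table S1 counts additional doses by group and visit interval with a control column, and N-protein IgG is a parallel definition measured in all participants. Both trial vaccines are spike-based, which makes N-protein a sensible cross-check. This gives useful context, but group totals in S1 do not show which spike-rule cases had a dose in the same interval. SAP 9.1 prints no N-protein threshold, and a separate N-protein count leaves the spike count as it was.

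Second, Table 13 may be incomplete in the text extracted from the PDF: it shows no missing-data or analysis-approach cell, unlike the other estimand tables, and the layout of Dummy Table 3 cannot be judged. This caution stands. The dose point rests mainly on 9.1, Table 12 and the Table 13 footnote, which read as complete.

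Third, a reader might infer that controls are simply given a shorter window. The documents do not support that as a flat statement. The start point may be there only to keep the trial-vaccine rise in A/B from counting, and Table 12's request for Group C at Month 6 could be met by pairing Day 0 with Month 6. On that reading C has slightly more time than A/B. What stands is that the SAP does not say which pair is used.

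Fourth, a reader might infer that controls or RAT-only cases would be dropped. That is unlikely: 9.1 says RAT or PCR, Table 12 compares A, B and C, and Table 13 lists the control arm. These are drafting contradictions to align.

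**Conclusion.** The point holds for the spike rule. As written, a recorded vaccine dose can be counted as an undocumented infection, and unequal uptake could create a group difference. Its size cannot be estimated from the documents; the 1.5 to 9.0 points per 10-point uptake difference is illustrative and depends wholly on the assumed *f* and *p*. The control start point is a secondary ambiguity with two outcomes (24 or 30.0 months against 29.1 to Month 30). The test and denominator wording is editorial.

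The consequence is confined to exploratory, descriptive endpoints. It would be wrong to infer that the Day-28 primary comparison is affected: no primary or secondary endpoint is defined by this rule. Still, SAP 4.8 treats breakthrough-infection data as essential to interpreting the immunological results, so the change is worth making.

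**What to change.** **Main change, in SAP 9.1 and Table 13.** Treat any interval containing a recorded extra COVID-19 vaccine dose (4th or later in controls, 5th or later in A/B) as not evaluable by the spike rule. State that this departs from Treatment Policy, which stays for test-confirmed infection. For each time-period, use participants with an evaluable interval as the denominator, and report the number of non-evaluable intervals by group. For cumulative risk, state how participants with some non-evaluable intervals are counted. Show the planned N-protein result alongside, with its threshold.

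**Start point.** Repeat it in Table 13. Make the three-group spike-rule comparison over intervals sampled in all groups (Month 6 onward), show Day 28 to Month 6 for A vs B only, and report the controls' Day 0 to Month 6 pair separately.

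**Alignment.** Change Table 13's first outcome to RAT or PCR, and its analysis set to all randomised participants plus all enrolled controls.

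**Cost.** Wording only: dose and positive-test dates are on the SAP 4.9 list of necessary variables, and SAP Table 3 has N-protein IgG measured in all participants. The price is fewer evaluable intervals, more observation time lost in the group with higher dose uptake, infections close to a dose missed by the spike rule, and some selection if people who take doses differ from those who do not. Reporting non-evaluable intervals by group makes this visible but does not remove it.

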9.2 ESTIMAND-TO-ANALYSIS TABLES FOR BREAKTHROUGH INFECTION ENDPOINTS

Table 13. Generic Estimand-to-Analysis table for all breakthrough infection endpoints for incidence risk (specified in Table 12).

Exploratory objective (as per Protocol): To describe the number and severity of breakthrough cases in the control group compared with the two vaccine groups (bivalent Moderna and Novavax)	
Estimand (for each trial vaccine):	Incidence risk of [OUTCOME] [*] to [TIMEPOINT] [*] , by trial vaccine in adults 18 years or older who have received their third dose of COVID-19 vaccine at least six months previously
ESTIMAND Attributes:	Incorporation of Estimand Attribute in ANALYSIS:
Treatment Bivalent mRNA Moderna COVID-19 vaccine and protein-based Novavax COVID-19 vaccine	Study arms Bivalent Moderna vaccine arm Novavax vaccine arm Control arm
Adults 18 years or older who have received their third dose of COVID-19 vaccine at least six months previously	Analysis set All randomised participants
Variable SARS-CoV-2 infection (breakthrough infection)	Outcome measure 1. Breakthrough infection as determined by at least one positive SARS-CoV-2 test (PCR) [^]

	2. Undocumented BTI as defined as a fold-change of ≥ 1.2 in spike-specific SARS-CoV-2 Wuhan IgG results between visits
Handling of intercurrent events	
Event	Strategy⁴
Receipt of 5 th dose (self-initiated)	Treatment Policy (interpret results in conjunction with 5 th dose coverage)
Population-level summary measure	
Incidence risk (proportion positive)	

*This table is generic for all breakthrough infection endpoints for incidence risks (with varying combinations of outcomes and timepoints) specified in Table 12, as they will be analysed in the same way.

⁴Analysis to be repeated for undocumented breakthrough infections

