4.9 Additional Consent

4.9.1 Extended Follow-Up Period: At or after the 12-month study visit, participants will be approached to provide consent for the continued collection of breakthrough infection information. This will involve monitoring any instances of breakthrough infections beyond the initial 12-month study period. The continuation of study procedures beyond the 18 month visit, including potential extensions up to 30 months, will be contingent upon the availability of future funding. Should additional funding be secured, the study intends to extend its duration to 30 months, incorporating blood collections at the 18, 24 and 30-month intervals. Participants will be asked to provide separate consent for these study procedures.

Extended Follow-up Period 2: Additional funding is available to collect a blood sample at 18 months and conduct some testing. The funding will cover the collection and biobanking of serum and PBMC samples (from CMI subset) and IgG testing. Further funding will be needed to complete the additional

immunological assays, including CMI assays. Funding applications for an NHMRC Ideas grant has been submitted. Participants will be asked to provide additional consent for the 18-month blood sample and for the continued collection of breakthrough information until 24 months. Participants will be informed prior to the 24-month visit whether this will occur in-person or via phone call. SMS messages will be sent to participants every 3 months to remind them to report any breakthrough infections.

Extended Follow-Up Period 3: We intend to extend the study to 30 months. The funding will cover the 24-month collection, biobanking of serum and PBMC samples (from CMI subset) and IgG testing. Further funding will be needed to complete the additional immunological assays, including CMI assays. A funding application for NIH has been submitted. Furthermore, funding for the additional 30-month visit is pending confirmation. If funding isn't secured participants will be informed and the scheduled 30-month appointments cancelled. We will ask participants to sign one consent form at the 24-month visit which includes the 30-month visit to avoid them having to sign another consent at 30-months again.

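### Breakthrough infection to Month 30 is specified as a simple proportion of all randomised participants, with no stated rule for people whose follow-up ends early

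*SAP*

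**What the plan says.** SAP section 9.2, Table 13, is the generic estimand table for all breakthrough endpoints. Its summary measure is "Incidence risk (proportion positive" and its analysis set is "All randomised participants", although the same table lists the control arm, which was not randomised. The timepoints in Table 12 (SAP section 9.1) are "To Day-28 visit; Month-6 visit; Month-12 visit; Month-18, Month-24, Month-30", and the comparison is "Group A vs Group B vs Group C Descriptive only". A Table 12 footnote says the analysis is repeated "for the risk and rate of breakthrough infection to that timepoint", but no person-time definition or estimand table for a rate follows.

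Protocol section 4.9 makes later follow-up conditional:

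- At or after Month 12, "participants will be approached to provide consent for the continued collection of breakthrough infection information".
- In the second extension, further consent is sought "for the continued collection of breakthrough information until 24 months".
- In the third, one form signed at the 24-month visit also covers the 30-month visit, which is cancelled if funding is not found.
- Of the later blood collections it says: "Participants will be asked to provide separate consent for these study procedures". This matters for the two breakthrough definitions that rest on IgG results.

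SAP section 6.5 classes loss to follow-up as missing data and points to section 4.10. The imputation there is for immunological endpoints only, and so are the analyses in Table 14.

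**The concern.** A proportion over everyone randomised is a valid risk only if everyone is observed to the timepoint. Here observation can end at 12, 18 or 24 months by design. An infection after that point is not recorded, yet the person still counts in the denominator if the table is applied as written.

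The exploratory objective is to describe breakthrough cases in controls beside the two vaccine groups. Group C is self-selected and not randomised, so equal retention cannot be assumed. If retention differs, the percentages will differ for that reason alone. Even a purely descriptive table would then mislead.

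**Working it through.** **The plan's own loss figure.** The only one is the allowance of about 20% in SAP section 3.5 (also Protocol section 11.1), within the Day-28 antibody sample size. It reproduces:

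- SD of log concentration = √ln(1 + 1.15²) = 0.918.
- n per arm = 2 × (1.960 + 1.282)² × 0.918² / (ln 1.4)² ≈ 157, against the stated 160.
- 160 / 0.80 = 200, as stated.

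This allowance concerns the Day-28 comparison and says nothing about loss by Month 30. No infection risk is given anywhere, so the inputs below are assumptions.

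**Assumed inputs.** T = 30 months; true 30-month risk p from 30% to 70%; loss by Month 30 d from 5% to 40%; constant hazards; loss independent of infection.

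**Literal reading (cases seen / everyone enrolled).** With λ = −ln(1−p)/T and μ = −ln(1−d)/T, the reported proportion is

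C = λ/(λ+μ) × [1 − (1−p)(1−d)].

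At d = 20%:

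| True risk | Calculation | Reported | Shortfall |
|---|---|---|---|
| 30% | 0.357/0.580 × 0.44 | 27.1% | 2.9 points |
| 50% | 0.693/0.916 × 0.60 | 45.4% | 4.6 points |
| 70% | 1.204/1.427 × 0.76 | 64.1% | 5.9 points |

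At a true 50%, losses of 5%, 10%, 30% and 40% give 48.9%, 47.7%, 42.9% and 40.3%.

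**Timing of loss** (true 50%, 20% lost). The risk by month t is 1 − 0.5^(t/30), which is 0.242, 0.340 and 0.426 at 12, 18 and 24 months.

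- All leave at Month 12: 0.8 × 0.5 + 0.2 × 0.242 = 44.8%.
- Equal thirds leave at 12, 18 and 24 months: 0.8 × 0.5 + 0.2 × (0.242 + 0.340 + 0.426)/3 = 46.7%.

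**Unequal loss.** With a true 50% in both groups, 10% against 30% loss gives 47.7% against 42.9%, a false gap of 4.8 points.

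**Other denominators** (true 50%, 20% lost).

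- Completers only: 50%, no bias while loss is independent of infection.
- Infections seen before leaving are kept but event-free leavers are dropped: 0.454 / (0.454 + 0.5 × 0.8) = 53.2%.

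**Check of the alternatives.** In a simulation of 400,000 participants at a true 50% and 20% loss, the crude proportion was 45.5%. Kaplan-Meier gave 50.1%, and the risk derived from the person-time rate also gave 50.1%.

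**The case against.** A reader might infer that the plan counts people who leave as uninfected and so understates the risk in every group. The documents do not support that as a statement of fact.

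- No section codes leavers as negative. SAP section 6.5 treats loss as missing data. Where the SAP does equate missing with no event, it says so explicitly, and only for reactogenicity (Table 7).
- Tables 6, 7, 9 and 10 have entries for missing data and analysis approach. None is visible in Table 13 as read, and the planned breakthrough display is largely not shown. Both may have been lost in text conversion, so their absence is weak evidence.
- The direction of bias depends on the denominator, as the working shows. The spike-IgG definition (a rise of 1.2-fold or more between visits) can also register a fifth dose as an infection, which pushes the figure upward.
- A rate is already promised, and it would deal with incomplete follow-up if person-time were defined.
- There is some mitigation. Data collected before withdrawal are kept (Protocol section on withdrawal of consent), reminders go out every three months (Protocol section on unscheduled visits), and missing data are reported by arm (SAP section 4.10).
- The endpoints are exploratory, and the contrast with Group C is confounded under any estimator.

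All of this limits the certainty and the consequence. It does not close the gap: the missing-data cross-reference ends in imputation that excludes this endpoint, the rate is undefined, and the stated measure does not suit censored follow-up.

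**Conclusion.** The point holds in a limited form. Table 13 states a simple proportion over all randomised participants to Month 30, for an outcome whose observation depends on repeated consent and on funding. Applied literally, it understates risk by about 3 to 6 points at 20% loss for true risks of 30% to 70%, and 10% against 30% loss creates a false difference of about 5 points at a true 50%. These sizes rest on assumed risks and losses, constant hazards, and loss independent of infection.

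Understatement is the consequence of the literal reading, not a certainty. The firmer conclusion is that the same data, with a true risk of 50% and 20% loss, could be reported as anything from about 45% to 53% depending on a denominator choice the SAP does not settle. Read literally, the analysis set also omits Group C. This merits an SAP amendment, at a priority that suits an exploratory, descriptive endpoint.

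**What to change.** - **Documented infection (RAT or PCR, as in SAP section 9.1; Table 13 names PCR only).** Replace the crude proportion with the Kaplan-Meier cumulative incidence of first infection at each Table 12 timepoint. Censor at withdrawal, end of consent or last contact. Give 95% CI and numbers at risk by group.
- **Rate.** Define the events and person-time for the rate promised in the Table 12 footnote.
- **Analysis set.** Word it so that it includes the non-randomised Group C.
- **Spike-IgG and N-protein definitions.** These infections can only be placed between two blood draws, so a Kaplan-Meier curve by test date does not apply. Report each visit interval among participants with samples at both visits.

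No new data are needed: SAP section 4.9 already requires the date of each positive test to be cleaned and locked, though the dates on which consent ended and of last contact must be available for censoring. The cost is a little more analysis work and a stated assumption that censoring is non-informative within group.
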